#### *Tumour Response Using PERCIST v1.0*

For phase I, tumour response will be evaluated using the PERCIST guideline v1.0 (see IRC). Only subjects with measurable disease at baseline, who have received at least two administrations of  $^{177}\text{Lu}$ -OPS201 and reached EOCT visit will be considered evaluable for response.

Key elements of PERCIST include performance of PET scans in a method consistent with the NCI recommendations (UPICT) and those of The Netherlands multicentre trial group on well calibrated and well-maintained scanners. A baseline PET scan will be obtained at approximately 1 hour (50 to 70 minutes) after  $^{18}\text{F}$ -FDG injection. At EOCT, the PET scan will be obtained with the same interval (between  $^{18}\text{F}$ -FDG-injection and acquisition time) reported at baseline  $\pm 15$  minutes, but never less than 50 minutes from the injection. All scans will be performed on the same PET scanner with the same injected dose  $\pm 20\%$  of radioactivity.

A PERCIST evaluation will also be performed using the  $^{68}\text{Ga}$ -OPS202 scans (mGa-PERCIST). This will provide a different set of analyses and support the possibility of using  $^{68}\text{Ga}$ -OPS202 as a surrogate endpoint in future studies.

Tumour metabolic response of each subject will be defined based on quantitative changes ( $\text{SUL}_{\text{max}}$  and  $\text{SUL}_{\text{mean}}$ ) in tumour-to-background after two cycles versus baseline and will be graded as complete metabolic response (CMR), partial metabolic response (PMR), stable metabolic disease (SMD) or progressive metabolic disease (PMD) or unevaluable according to PERCIST v1.0. The grading scale for “mGa-PERCIST” will be evaluated.

#### *Sstr2 Targeted Tumour Uptake*

Sstr2 targeted tumour uptake will be determined using PET/CT molecular imaging with the companion diagnostic imaging product  $^{68}\text{Ga}$ -OPS202.

The change in  $^{68}\text{Ga}$ -OPS202 PET/CT tumour uptake will be computed as a change in  $\text{SUV}_{\max}$  and  $\text{SUV}_{\text{mean}}$  from baseline to EOCT/EOAC visit. These changes will also be compared to clinical outcome and ORR and to  $^{177}\text{Lu}$ -OPS201 tumour uptake on SPECT/CT.

## Phase II

The primary endpoint is ORR over the two treatment cycles of the core study. Objective response is defined using RECIST v1.1 measured by CT or magnetic resonance imaging (MRI). Tumour response assessments are performed 6 weeks after each administration of  $^{177}\text{Lu}$ -OPS201 during the core study or at the time of occurrence of first clinical signs of disease progression as determined by the investigator. Radiological interpretation for subject management will be performed at the site, whereas efficacy evaluation will be conducted by the ICL.

Primary and secondary tumour activity endpoints and evaluations are summarised in Table 2.

**Table 2 Primary and Secondary Tumour Activity Endpoints and Evaluations**

Measure	Timepoint	Variable	Endpoint
Tumour size (longest diameter)	Screening [a] and 6 weeks after each $^{177}\text{Lu}$ -OPS201 administration (each cycle)	Tumour response according to RECIST v1.1	
 
ORR
 
BOR
 
PFS (complemented with events of death)
 
DRR (CR or PR lasting <math>\geq 6</math> months)
 
DCR
 
TTP
 
TTR
 
DoR
 

Tumour size (longest diameter)	Screening [a] and 6 weeks after second $^{177}\text{Lu}$ -OPS201 administration (second cycle)	Tumour response according to mGa-RECIST; Metabolic tumour response by $^{18}\text{F}$ -FDG-PET – PERCIST v1.0 and $^{68}\text{Ga}$ -OPS202 by mGa-PERCIST*	
 
ORR
 
BOR
 

Tumour volume	Screening [a] and 6 weeks after each $^{177}\text{Lu}$ -OPS201 administration (each cycle)	Mean change (%) in tumour volume assessed by volumetric CT/MRI	% change from baseline in tumour volume
Event of death	1 and 2 years	Death count	OS
$\text{SUV}_{\max}$ and $\text{SUV}_{\text{mean}}$	Screening [a] and 6 weeks after second $^{177}\text{Lu}$ -OPS201 administration (second cycle)	sstr2 targeted tumour uptake by $^{68}\text{Ga}$ -OPS202- PET/CT	Change in tumour uptake on $^{68}\text{Ga}$ -OPS202 PET/CT scan

Measure	Timepoint	Variable	Endpoint
SUL max and SUL mean	Screening [a] and 6 weeks after second  Lu-OPS201 administration (second cycle)	Tumour-to-background ratio by  F-FDG-PET using PERCIST v1.0	Quantitative changes in tumour-to-background  F-FDG-PET uptake
SUV max and SUV mean	Screening [a] and 6 weeks after second  Lu-OPS201 administration (second cycle)	 Ga-OPS202 uptake and  Lu-OPS201 therapy response	Change in  Ga-OPS202 uptake on PET scan in subjects screened for  Lu-OPS201 treatment as compared to clinical response and ORR
SUV max and SUV mean	Screening [a] for  Ga-OPS202 PET/CT; Screening [a] and 6 weeks after second  Lu-OPS201 administration (second cycle)	Uptake on  Ga-OPS202 PET/CT and  Lu-OPS201 therapy response (using ceCT/MRI – RECIST v1.1)	Correlation between the uptake on  Ga-OPS202 PET/CT at baseline [a] with tumour response to  Lu-OPS201 therapy
Lesion count	For  Ga-OPS202 at screening For  Lu-OPS201 at 24 hours after first administration (Cycle 1)	Uptake on  Ga-OPS202-PET/CT and uptake on  Lu-OPS201 SPECT/CT	Correlation between the uptake of  Ga-OPS202 in tumour lesions expressing sstr2 on PET/CT images and the uptake on  Lu-OPS201 SPECT/CT
Identification of avid lesions	Screening [a]	Number of subjects with avid lesions	Proportion of subjects with sstr2-positive tumour lesions by  Ga-OPS202 PET/CT

Abbreviations: ce= Contrast enhanced; CR=Complete response; CT=Computed tomography; DCR=Disease control rate; DoR=Duration of response; DRR=Durable response rate; FDG=Fluorodeoxyglucose; MRI=Magnetic resonance imaging; OS=Overall survival; PERCIST=Positron emission tomography response criteria in solid tumours; PET=Positron emission tomography; PFS=Progression free survival; PR=Partial response; RECIST=Response evaluation criteria in solid tumours; SUL=SUV normalised by lean body mass; SUV=Standardised uptake volume; TTP=Time to progression; TTR=Time to response.

[a] Screening=Baseline scan

Patient Reported Outcomes (PROs) will be assessed in phase II using the following questionnaires: the EuroQoL 5-dimension 5-level (EQ-5D-5L) and European Organization for Research and Treatment of Cancer Quality of Life Questionnaire Core 30 (EORTC QLQ-C30).

The EQ-5D-5L questionnaire is a 2-page, generic preference-based Quality of Life (QoL) measure comprised of a 5-item health status measure and a visual analogue scale and is used to generate two scores. The EQ-5D utility score is based on answers to five questions to evaluate mobility, self-care, usual activities, pain/discomfort and anxiety/depression. Each dimension has 5 levels: no problem, slight problems, moderate problems, severe problems, unable to/extreme.

The EQ-5D-5L visual analogue scale generates a single health status index, the analogue scale ranges from 0 to 100 in which subjects are asked to rate their current health state by drawing a line from a box marked.

The EORTC QLQ-C30 is a 2-page, self-reporting 30-item generic instrument for use in cancer subjects across tumour types. It assesses 15 domains consisting of five functional domains (physical, role, emotional, cognitive, social), nine symptom domains (fatigue, nausea and

vomiting, pain, dyspnoea, insomnia, appetite loss, constipation, diarrhoea, financial difficulties) and a global health status or QoL scale as shown below. Missing data will be handled using the method described in the scoring guidelines for EORTC QLQ-C30. If at least half of the items from a scale are answered, it is assumed that the missing items have values equal to the average of those items that are present for that respondent.

Table 3 Scoring EORTC QLQ-C30 version 3.0

	Number of items	Item range	Item numbers
Global health status/QoL			
Global health status/QoL	2	6 (1-7)	29, 30
Functional scales			
Physical functioning	5	3 (1-4)	1-5
Role functioning	2	3 (1-4)	6, 7
Emotional functioning	4	3 (1-4)	21-24
Cognitive functioning	2	3 (1-4)	20, 25
Social functioning	2	3 (1-4)	26, 27
Symptom scales / items			
Fatigue	3	3 (1-4)	10, 12, 18
Nausea and vomiting	2	3 (1-4)	14, 15
Pain	2	3 (1-4)	9, 19
Dyspnoea	1	3 (1-4)	8
Insomnia	1	3 (1-4)	11
Appetite loss	1	3 (1-4)	13
Constipation	1	3 (1-4)	16
Diarrhoea	1	3 (1-4)	17
Financial difficulties	1	3 (1-4)	28

The PK of Lu-OPS201 and OPS201, as well as the dosimetry assessments and timepoints are related to the phase I of the study. PK and dosimetry assessments will also be included in phase II. However, the timepoints might be revised based on the phase I results and document as part of a protocol amendment.

### 1.3.2.2 Safety assessments

The primary safety variable is the occurrence of Dose-Limiting Toxicities (DLTs) during Cycle 1 or Cycle 2.

The DLTs are defined for any of the following Investigational Radio-Pharmaceutical Product-related (IRPP-related) AEs according to National Cancer Institute Common Terminology Criteria Adverse Event (NCI-CTCAE) scale version 5.0 that occur during the defined DLT assessment period (from the first administration of Lu-OPS201 to 6 weeks after the second administration):

- Grade 4 neutropenia lasting for seven or more consecutive days.
- Grade 3 and 4 febrile neutropenia.
- Grade 4 thrombocytopenia for seven or more consecutive days.
- Grade 3 thrombocytopenia complicated by a bleeding event.
- Grade 4 anaemia.

- Grade 3 anaemia requiring transfusion.
- Grade 3 or higher laboratory abnormalities of aspartate amino transferase/alanine amino transferase (AST/ALT) and/or bilirubin, with the following exceptions:
  - for subjects with Grade 1 AST/ALT at baseline (>upper limit of normal (ULN) to 3xULN), a AST/ALT level of >7.5xULN will be considered a DLT.
  - for subjects with Grade 2 AST/ALT at baseline (>3xULN to 5xULN), a AST/ALT level > 10xULN will be considered a DLT.
- any Grade 3 or higher acute kidney injury (creatinine >3x baseline or >4.0 mg/dL).
- Grade 3 or higher non-haematological toxicity excluding:
  - Grade 3 nausea, vomiting or diarrhoea for less than 72 hours with adequate supportive care
  - Grade 3 fatigue lasting less than a week
  - Grade 3 or higher electrolyte abnormality that lasts for less than 72 hours, is not clinically complicated and resolves spontaneously or with conventional medical interventions
  - Grade 3 or higher amylase or lipase not associated with symptoms or clinical manifestations of pancreatitis
- any toxicity related to Lu-OPS201 resulting in a treatment delay of more than 4 weeks due to delayed recovery to baseline or resolution of any AE of Grade 2 or more (exception of alopecia and lymphopenia).
- Grade 5 toxicity (death)

**DLT Assessment:** During the DLT assessment period (from first administration of Lu-OPS201 to 6 weeks after the second administration), two assessments over 6 weeks each will be performed. The first, between first and second administration and the second, between second administration and EOCT visit.

**DLT Population:** Subjects will be evaluable for DLT if received Cycle 1 and Cycle 2 administrations and completed DLT assessment period (i.e. 6 weeks after second administration) or stopped treatment because of a DLT during DLT assessment period.

Other safety assessments include clinical laboratory haematology, serum chemistry, urinalysis and pregnancy tests, physical examination, vital signs, electrocardiography.

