- Subject has not sufficiently recovered from an adverse event despite extension of the dosing interval by 4 weeks (such as delayed grade 3-4 haematotoxicity)
- Hypersensitivity to the active substance or to any of the excipients of the study drugs
- Radiological disease progression

All cases of discontinuation will be discussed between the investigator and the sponsor.

A subject can also withdraw their consent to the treatment period but agree to take part in 24-month follow-up period.

If a subject is considered Not Evaluable for DLT due to withdrawal during DLT assessment period, he/she will be replaced by another subject.

In phase I, a cohort will be considered as completed once three subjects of the cohort complete Cycle 2 or discontinue early during Cycle 2. If subjects discontinue for any reason other than a DLT (e.g. disease progression) before end of Cycle 2, they might be replaced.

The phase I will be terminated once the MTCA has been determined. The phase II is designed with early stopping criteria, allowing any cohort to be closed early in case of futility.

A specific site or a given cohort can also be discontinued or the entire study may be terminated at any time if the sponsor judges it necessary for any reason. In that case, all scheduled procedures and assessments for subjects who are still in the study will be performed. Some possible reasons for the closure of a study site may include:

- failure of the investigator staff to comply with the protocol or with the Good Clinical Practice (GCP) guidelines.
- safety concerns.
- inadequate subject recruitment.

In case of premature discontinuation of a site or the complete study, depending on the reason(s) for the discontinuation, the sponsor will notify the investigator(s) affected in writing as to whether the ongoing subjects should continue the remaining IRPP dose administration(s).

Should, at the start of the study, 20 consecutive subjects fail screening due to Ga-OPS202 PET/CT negative for sstr2 with all the other inclusion/criteria met, the administration of Ga-OPS202 and subsequent PET imaging will be stopped. Selection of sstr2-positive tumours for the treatment with Lu-OPS201 will be revised in a protocol amendment.

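### In the DLT list, Grade 4 thrombocytopenia of under 7 days with a bleed below Grade 3 meets no platelet or bleeding criterion, although Grade 3 thrombocytopenia with the same bleed is a DLT

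*SAP*

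**What the plan says.** SAP Section 1.3.2.2 names DLT occurrence in Cycle 1 or 2 as the primary safety variable. Meeting any single bullet of the list is enough, provided the event is related to the investigational radiopharmaceutical.

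**Platelets.** There are two bullets: "Grade 4 thrombocytopenia for seven or more consecutive days" and "Grade 3 thrombocytopenia complicated by a bleeding event". The first does not mention bleeding. The second names Grade 3 alone and sets no minimum grade for the bleed.

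**Other bullets that could catch the same subject.** These are Grade 4 anaemia without condition, Grade 3 anaemia that needs transfusion, any related toxicity "resulting in a treatment delay of more than 4 weeks due to delayed recovery to baseline" (or due to resolution of an AE of Grade 2 or more), and the general bullet, "Grade 3 or higher non-haematological toxicity excluding" four named items.

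**Liver.** Grade 3 or higher AST/ALT or bilirubin is a DLT, with two exceptions. For a Grade 1 baseline, "a AST/ALT level of >7.5xULN will be considered a DLT". The other reads: "for subjects with Grade 2 AST/ALT at baseline (>3xULN to 5xULN), a AST/ALT level > 10xULN will be considered a DLT". AST/ALT is not among the four exclusions of the general bullet.

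**Use of the flag.** Section 3.1.1 caps the share of subjects with a DLT at 33% in the MTCA definition. The flag also feeds the data review board tables (Section 3.2.2) and the Bayesian model (Sections 3.2.2.3 and 3.2.16). A subject is DLT-evaluable on completing the assessment period, or having "stopped treatment because of a DLT during DLT assessment period". Section 1.3.2.10 adds: "If a subject is considered Not Evaluable for DLT due to withdrawal during DLT assessment period, he/she will be replaced by another subject".

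**The concern.** A toxicity list should not count a milder event and pass over a worse one in otherwise equal circumstances. The two platelet bullets allow this. Bleeding is tied to Grade 3 only, and Grade 4 is tied to duration only, so a short Grade 4 episode with a minor bleed falls between them.

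The drafting elsewhere in the list makes it unsafe to read the bare Grade 3 as a minimum. The febrile neutropenia bullet names Grades 3 and 4, and several bullets say Grade 3 or higher. The anaemia pair has no such gap, because Grade 4 anaemia counts unconditionally.

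At stake is the yes/no DLT flag of a subject in escalation. A missed flag lowers the observed DLT rate and so errs towards escalation. If the subject also stops treatment early because of the event, the missing flag makes the subject not evaluable for DLT, and the subject is replaced.

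**Working it through.** The document gives no figure to reproduce. The check applies the bullets of Section 1.3.2.2 to each combination.

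**1. Platelets.** Inputs are thrombocytopenia grade (3 or 4), duration (under 7 days, or 7 days or more) and bleed (none, below Grade 3, Grade 3 or higher). Assumptions: the event is product-related, each episode has one grade, a bleed of Grade 3 or higher counts under the general non-haematological bullet, and no anaemia or delay bullet is met.

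| Duration | Bleed | Grade 3 platelets | Grade 4 platelets |
|---|---|---|---|
| under 7 days | none | no DLT | no DLT |
| under 7 days | below Grade 3 | **DLT** | **no DLT** |
| under 7 days | Grade 3 or higher | DLT | DLT (general bullet) |
| 7 days or more | none | no DLT | DLT |
| 7 days or more | below Grade 3 | DLT | DLT |
| 7 days or more | Grade 3 or higher | DLT | DLT |

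One of 2 x 3 = 6 comparisons is inverted. If a delay of more than 4 weeks is present, both columns are DLTs in every row. Over 2 x 3 x 2 = 12 comparisons with delay no/yes, the count is therefore still one. Grade 4 anaemia or transfused Grade 3 anaemia closes the gap in the same way. So does a bleed on days when the count is at Grade 3, because the one-grade assumption then fails and the Grade 3 bullet applies.

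**2. Weight of one flag.** Section 1.3.4 gives 3 to 5 subjects per cohort. One flag is 1/3 = 33.3%, 1/4 = 25% or 1/5 = 20% of the cohort.

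**3. AST/ALT (secondary).** The SAP cites CTCAE version 5.0 but does not print where Grade 3 begins, so two assumptions bracket the overlap between the general bullet and the exceptions.

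- *Assumption A: Grade 3 starts at a fixed 5xULN*, as the printed Grade 2 band (ending at 5xULN) suggests. For a Grade 1 baseline the width is 7.5 - 5 = 2.5xULN. For a Grade 2 baseline it is 10 - 5 = 5xULN.
- *Assumption B: Grade 3 starts at 5 times an abnormal baseline b (in xULN).* For a Grade 1 baseline the width is max(0, 7.5 - 5b): b = 1.1 gives 2.0, b = 1.2 gives 1.5, b = 1.4 gives 0.5, and b of 1.5 or more gives 0. For a Grade 2 baseline b exceeds 3, so Grade 3 starts above 15xULN, beyond the 10xULN limit, and the width is 0.

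The overlap thus runs from none to 5xULN wide, depending on a grading convention that the document does not state.

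**The case against.** The strongest reply is that the gap is narrow and the people applying the rule would see through it. A data review board may well read Grade 3 as a minimum. It also reviews all available safety and dosimetry data, so a Grade 4 platelet event with bleeding would be seen whatever its flag. When DLTs occur, escalation is guided by Bayesian modelling and not by a cut-off on one cohort's raw rate. The list stands in Section 1, which reproduces the protocol, and the protocol or the separate Bayesian plan may already settle the point. Section 5 keeps only selected listings after premature closure. None is a DLT output, and the listing of AEs of Grade 3 or above would show such an event anyway.

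Most of this stands, and it limits the weight of the point. It does not make the printed rule right: the sensible reading is not the written one, and the flag is what the evaluability rule and the model use. The delay bullet is also a weak safeguard. It turns on the length of a delay and not on the bleed, and after the second administration only optional additional cycles remain to be delayed.

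On AST/ALT the reply is stronger. The two exceptions would have little or no force if the general bullet recaptured the same values, so the specific bullet must be meant to govern. Acute kidney injury likewise has its own bullet beside the general one, without harm. What remains is only that precedence is not written down.

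**Conclusion.** The DLT definition is wrong as written, and the point is minor. One combination is misordered: Grade 4 thrombocytopenia under 7 days, a bleed below Grade 3 confined to Grade 4 days, and no other bullet met. The conclusion rests on taking the bare Grade 3 literally, which the wording of neighbouring bullets supports. The document does not show how often this would occur. With no DLT output retained, the practical effect now is small.

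Four stronger readings are not supported:

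- *That only the delay bullet could rescue the case.* The anaemia bullets and a bleed on Grade 3 days also can.
- *That the general bullet cancels the AST/ALT exceptions.* The likely intent is the reverse, and the size of any overlap rests on an unprinted convention.
- *That one missed flag would change a dose decision.* The 33.3, 25 and 20 points are shifts in an observed cohort rate only.
- *That the subject drops out of the phase I primary analysis.* Under Sections 2.4 and 2.7 that analysis uses every escalation subject who received at least one dose. Only the flag changes.

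**What to change.** 1. In the bullet that ties thrombocytopenia to bleeding, insert *or higher* after *Grade 3*. The short Grade 4 case with a minor bleed then counts, and no row of the table is inverted.
2. As a clarification only, add AST/ALT and bilirubin to the exclusions of the general non-haematological bullet, stating that they are assessed solely under their own bullet. This preserves the 7.5xULN and 10xULN limits under either grading convention.
3. Make the same edits in the protocol and in the separate Bayesian analysis plan if they carry the same list, so that the SAP does not depart from its source.

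The cost is two wording changes, repeated where the list recurs. No extra data or analysis is needed.

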### **1.2.2 Study exposure**

In phase I, for subjects receiving only two treatment cycles of  $^{177}\text{Lu}$ -OPS201, this study will consist of up to 3-week screening period and a 12-week dosing period (+ up to additional 4 weeks in case of adverse events (AEs) that need to be adequately recovered). A treatment cycle is defined as the timeframe of 6 (up to 10) weeks between two administrations or the timeframe of 6 weeks following the last administration. In case of logistical issues, the cycle could be extended by up to additional 2 weeks. Dosing period can be extended up to 36 weeks in case subjects receive up to four additional cycles. Subjects are thus expected to participate in this study for a minimum of 15 weeks and up to 39 weeks (+ up to additional 4 weeks in case of AEs that need to be adequately recovered). In all cases, a long-term follow-up lasting 24 months will start after the end of the last  $^{177}\text{Lu}$ -OPS201 cycle.

For phase II, it is anticipated that the duration of the study will be identical to the duration in phase I; however, pending the results of phase I on recommended treatment regimen (doses and intervals) the study duration will be refined.

The subject's participation in the treatment period of the study will be considered to have ended at the end of core trial (EOCT) or end of additional cycles (EOAC) visit. The subject's participation in the 24-month follow-up period of the study will be considered to have ended when the subject dies, withdraws consent to the follow-up period, or ends the 24-month follow-up, whichever occurs first.

The overall duration of the study will be approximately 5.5 years. The study will be considered to have started when the first site has been initiated.

The study will be considered to have ended after the last subject has completed the last follow-up visit in the study.

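### DLT evaluability for early leavers rests on stopping treatment because of a DLT, not on having had one, which conflicts with the DLT endpoint and the MTCA evaluable population

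*SAP*

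**What the plan says.** SAP section 1.3.2.2 gives two routes into the DLT population. The first is to have "received Cycle 1 and Cycle 2 administrations and completed DLT assessment period (i.e. 6 weeks after second administration"). The second, for everyone else, is to have "or stopped treatment because of a DLT during DLT assessment period".

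The same section defines a DLT by occurrence: a listed, product-related event between the first administration and 6 weeks after the second. The list includes "Grade 5 toxicity (death"). Section 3.1.1 likewise defines the MTCA by the share of subjects who experience a DLT, with a limit of 33%.

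Section 1.3.2.10 has two replacement sentences. One is mandatory: "If a subject is considered Not Evaluable for DLT due to withdrawal during DLT assessment period, he/she will be replaced by another subject". The other is optional: "If subjects discontinue for any reason other than a DLT (e.g. disease progression) before end of Cycle 2, they might be replaced".

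The DLT population does not appear among the analysis sets of section 2. Sections 2.4 and 2.7 base the MTCA and the phase I primary analysis on the MTCA evaluable population, which is every subject with at least one dose in the radioactivity escalation.

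**The concern.** For a subject who does not complete the window, evaluability depends on why treatment stopped, while the endpoint depends on whether an event happened. The two can differ. A subject can have a DLT that does not itself end treatment and then leave because of progression or withdrawal of consent. That subject has contributed the information the cohort was set up to collect, yet is not DLT-evaluable. If the exit is a withdrawal, the subject must be replaced, and neither replacement sentence makes an exception for a DLT already observed.

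Cohorts hold 3 to 5 subjects (section 1.3.4), so one subject can decide on which side of 33% a cohort falls. Excluding a subject who had a DLT can never raise the observed rate, so any error is in the direction of under-counting toxicity. The plan also carries two different denominators for one endpoint and never says where the DLT population is used.

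**Working it through.** Phase I has no formal sample-size calculation (section 1.3.4), so there is no stated figure to reproduce. The check has two parts.

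**1. Cases against the two routes**

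Inputs: the two routes and the DLT list in section 1.3.2.2; the cycle definition in section 1.2.2; the cohort and replacement rules in section 1.3.2.10; the analysis sets in sections 2.4 and 2.7. All cases are escalation subjects who have had a DLT in the window.

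| Case | Window completed? | Stopped because of a DLT? | DLT population | MTCA evaluable |
|---|---|---|---|---|
| A. Both doses, reaches week 6 | Yes | Not needed | In | In |
| B. Treatment stopped in Cycle 1 because of the DLT | No | Yes | In | In |
| C. Leaves in either cycle, before week 6 after dose 2, for another reason | No | No | **Out** | In |
| D. Dies of the DLT, or leaves because of it, after dose 2 and before week 6 | No | Unclear | **Unclear** | In |

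Case C is a definite gap. Case D depends on what stopping treatment means once the last core infusion has been given. If treatment means infusions, none is left to stop and the subject is out. But section 1.2.2 defines a cycle as also running for a further period, "or the timeframe of 6 weeks following the last administration", and says that a subject's "participation in the treatment period of the study will be considered to have ended at the end of core trial (EOCT") or additional-cycles visit. Section 1.3.2.10 also recognises subjects who "complete Cycle 2 or discontinue early during Cycle 2". On that usage, case D can be read as stopping because of a DLT.

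**2. Effect of one such subject in a cohort**

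Let *d* be the number of DLTs among *n* dosed subjects.

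- All counted: *d*/*n*
- DLT subject dropped: (*d*−1)/(*n*−1)
- Dropped and replaced by a DLT-free subject: (*d*−1)/*n*
- DLT kept and a DLT-free replacement added: *d*/(*n*+1)

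| *n*, *d* | All counted | Dropped | Dropped and replaced | Kept, replacement added |
|---|---|---|---|---|
| 3, 1 | 1/3 = 33.3% | 0/2 = 0% | 0/3 = 0% | 1/4 = 25.0% |
| 4, 2 | 2/4 = 50.0% | 1/3 = 33.3% | 1/4 = 25.0% | 2/5 = 40.0% |
| 5, 1 | 1/5 = 20.0% | 0/4 = 0% | 0/5 = 0% | 1/6 = 16.7% |
| 5, 2 | 2/5 = 40.0% | 1/4 = 25.0% | 1/5 = 20.0% | 2/6 = 33.3% |

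The direction is general: (*d*−1)/(*n*−1) ≤ *d*/*n* is equivalent to *d* ≤ *n*, which always holds.

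Against the 33% limit, the clear crossings are 2/5 (dropped, with or without replacement) and 2/4 (dropped and replaced). The 1/3 cohort sits at the limit, so whether it crosses depends on whether 33% means 0.33 or one third. The 1/5 cohort is below the limit throughout. In the last column no event is lost; the rate falls only because the denominator grows by a subject without a DLT.

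**The case against.** Several points on the other side stand.

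- A reader might infer that a DLT counts only if it stopped treatment. It does not: anyone who completes the window is evaluable and their DLT counts (case A).
- A reader might infer that fatal DLTs are excluded. The SAP does not say so. Sections 1.2.2 and 1.3.2.10 support reading a death or DLT-driven exit in Cycle 2 as stopping because of a DLT, the mandatory replacement sentence is triggered by withdrawal rather than death, and the optional one sets DLT exits apart. The text is ambiguous on this point.
- A reader might infer that observed DLTs are lost from the primary analysis. Sections 2.4 and 2.7 use every dosed escalation subject, with no completion condition. Section 3.2.2.3 does not restrict the DLT summary to the DLT population, and section 3.2.16 has the data review board look at all available data.
- When DLTs are reported, activity selection is guided by a Bayesian model rather than raw cohort fractions. Its details are in a separate plan and a protocol appendix, neither of which is at hand, and they may settle the denominator.
- Section 5 limits the report to listings after premature closure; no DLT-rate or MTCA output is selected.

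These points narrow the finding without removing it. Case C still meets neither route, replacement is still tied to DLT evaluability whichever set is analysed, and the SAP still defines two sets for one endpoint without saying which serves cohort or board counts.

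**Conclusion.** The point holds in limited form. The evaluability rule in section 1.3.2.2 leaves out a subject with an observed DLT who exits early for another reason, requires replacement if the exit is a withdrawal, and is ambiguous for a fatal DLT or a DLT-driven exit after the second dose. It is inconsistent with the occurrence-based definitions in sections 1.3.2.2 and 3.1.1 and with the MTCA evaluable population in sections 2.4 and 2.7.

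The size depends on which set is used. If cohort or board counts use the DLT population, one dropped and replaced subject can move 2/5 (40%) to 1/5 (20%), across the 33% limit. If the MTCA evaluable population is used, the DLT stays and a DLT-free replacement moves 1/3 (33%) to 1/4 (25%). The counts are illustrative and assume that the replacement has no DLT; the SAP gives no basis for how often this would happen. In this study, closed early and reported through listings, the practical effect is small. The rule matters mainly as wording that should not be carried forward.

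**What to change.** 1. In section 1.3.2.2, define as DLT-evaluable any subject who has a DLT in the assessment period, regardless of whether the period was completed and of the reason for exit. This also settles the fatal case.
2. State that this DLT stays in both numerator and denominator even if another subject is added to the cohort.
3. Reconcile the DLT population with the two replacement sentences in section 1.3.2.10 (one mandatory, one optional) and with sections 2.4 and 2.7, and state which set serves the cohort and data review board counts.
4. Align the protocol text, because section 1 of the SAP is presented as taken from the protocol and a change in the SAP alone could create a new discrepancy.

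The cost is about one sentence of new wording plus cross-references, with a matching protocol clarification. No new data or analysis is needed.
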